All available data, including adverse events, changes in laboratory values and other safety parameters will be evaluated for each dose cohort in Part 1, in addition to futility and success analyses, and for each expansion cohort in Part 2.

Section 12.3.4 Interim Analysis

REVISED TEXT

12.3.4.1 Part 1

~~No formal interim analysis will be performed for Part 1 of the study. Safety, PK, and PD marker data will be examined during Part 1. Prior to determining the GSK2816126 dose for the next cohort, exploratory analyses will be conducted to assess the relationship of GSK2816126 dose levels with safety, PK and PD parameters using all data from available cohorts.~~

Futility and efficacy interim analysis of overall response rate will be performed continuously for GCB-DLBCL expansion cohort in Part 1 of the study, after 13 subjects have been enrolled. In addition, safety, PK, and PD marker data will be examined during Part 1. Prior to determining the GSK2816126 dose for the next cohort, exploratory analyses will be conducted to assess the relationship of GSK2816126 dose levels with safety, PK and PD parameters using all data from available cohorts. If success criteria are reached at an interim analysis for GCB-DLBCL at MTDRP2D twice-weekly every 3 out of 4 weeks followed by 1 week off, and the totality of data support opening Part 2, then Part 2 will begin and Part 1 expansion will close.

Full details of procedures and of the analyses planned at the interim analysis will be provided in the Reporting and Analysis Plan (RAP).

Section 12.3.4 Interim Analysis

REVISED TEXT

Section 12.3.4.2 Part 2

For each expansion cohort, after the initial ~~12-10~~ subjects have enrolled at the RP2D dose, response data will be reviewed on an ongoing basis and the number of responses observed will be compared with the stopping rules provided in Section ~~3.4~~12.2.2.. In

addition, safety, PK, and PD marker data will be analyzed. Full details of procedures and of the analyses planned at the interim analysis will be provided in the Reporting and Analysis Plan (RAP).

Section 12.4.1.4 Efficacy Analyses

REVISED TEXT

Anti-tumor activity for lymphoma subjects will be assessed based on the Response Criteria listed in Section 15.4. Anti-tumor activity for subjects with solid tumors will be assessed based on the Response Criteria listed in 15.5. Anti-tumor activity for subjects with MM will be assessed based on the Response Criteria listed in 15.6. Anti-tumor activity for subjects with prostate cancer will be assessed based on the Response Criteria listed in 15.7. The response data will be summarized by study part, and cohort within Part 2. Full details will be specified in the RAP.

Section 14 REFERENCES

Rationale for Change: Included new references and reformatted list. Moved references for appendices to the appropriate appendix.

REVISED TEXT

Dardenne *et al.*, 2016, *Cancer Cell* 30, 563–577

GlaxoSmithKline Document Number 2013N169204 _04. Version 04. GSK2816126 Investigator's Brouchure. Report Date: 25-Jan-2017

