The primary objective of Part 2 is to investigate whether administration of GSK2816126 at the RP2D has a potentially clinically meaningful activity for more tumor types, if notable response rate is observed in Part 1 expansion cohort of GCB-DLBCL patients. Expansion cohorts will be enrolled in Part 2, including GCB-DLBCL and tFL patients with mutant and wild type EZH2 and patients with MM. Similar to Part 1 expansion design, Part 2 expansion design is planned based on predictive probability methodology. Rather than early stop for either futility or efficacy, Part 2 allows early stop for futility only. For each expansion cohort of GCB-DLBCL and tFL patients, a minimum of 10 and maximum of 32 patients will be enrolled at the RP2D. For MM cohort, a minimum of 14 and maximum of 40 patients will be enrolled at the RP2D. Interim analysis of response data will start from minimum number of patients enrolled and at any time thereafter. Details of Part 2 designs and stopping criteria are elaborated in Section 12.2. All available data will be considered in making decision of termination or continuation of the trial.

It is noted that patients with GCB-DLBCL, tFL and MM enrolled at MTD/RP2D in the previous stages of the trial (dose escalation and cohort expansion in Part 1) will be included for the Part 2 analysis.

Lymphoma subjects will be enrolled based on EZH2 mutation status. There will be up to 30 subjects per group in both GCB-DLBCL cohorts, up to 16 subjects per group in both tFL cohorts, and up to 37 subjects with MM. Multiple myeloma subjects will be selected independent of their EZH2 mutation status.

Further evaluation of futility:

The methodology is based on the predictive probability of success if enrollment continues until all planned subjects are recruited [Lee, 2008]. The predictive probability design is similar to a Green Dahlberg design in that it allows for early stopping for futility. The differences are that the predictive probability design allows for evaluation of stopping rules after each subject, rather than at only two stages, once a minimum number of subjects are evaluable. In this particular study, we will stop only for futility. While the two designs have similar type I and type II error rates, the probability of early termination is greater with the predictive probability design.

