~~For Part 2, hypothesized response rates are provided in Section 12.2.2. In this case, a test that the response rate is less than or equal to the null hypothesis rate is being performed using the stopping rules provided in Section 3.4. Descriptive statistics will be used to describe the observed response rates at the RP2D dose used in the expanded cohorts.~~

Section 12.2 Sample Size Determination

REVISED TEXT

The sample size planned for Part 1 arises from the predefined criteria for dose selection and is not driven by statistical considerations.

In addition, Part 1 expansion may include up to 27 GCB-DLBCL subjects at MTD/RP2D twice-weekly for 3 out of 4 weeks followed by 1 week off. This will allow futility/success analysis with type I error rate no more than 0.1 and at least 80% of power. Additionally, 15 subjects with solid tumors or prostate cancer may be enrolled for the evaluation of safety, futility and efficacy.

The additional ~~129~~ 168 subjects in Part 2 of the study (which includes ~~approximately 30~~ up to 32 subjects each for the EZH2 mutant and EZH2 WT GCB-DLBCL populations, and ~~16~~ subjects each for the ~~up to 32 subjects each for~~ EZH2 mutant and EZH2 WT tFL populations as well as up to ~~37~~ 40 MM subjects) will provide additional safety and tolerability information about the treatment and a better precision around the response rate estimate.

Approximately 168 subjects will be enrolled in Part 2 in five expansion cohorts: two GCB-DLBCL cohorts with up to 32 subjects from the EZH2 wild-type population, and up to 32 subjects from the EZH2 mutation positive population, and two tFL cohorts with up to 32 subjects from the EZH2 wild-type population and up to 32 subjects from the EZH2 mutation positive population and up to 40 subjects in the MM cohort. Additional subjects/cohorts may be enrolled to allow for evaluation of additional dose levels.

Section 12.2.1 Part 1: Dose-Escalation Phase

REVISED TEXT

12.2.1.1 Dose Escalation in Part 1

The total number of subjects to be enrolled for dose escalation in Part 1 will depend on the number of subjects needed to characterize individual dose cohorts. The sample size is not driven by statistical considerations. However, it is anticipated that approximately 40 subjects will be enrolled. Given true incidence rates of DLTs, the associated probabilities of escalating to the next dose in a 3+3 scheme are provided for reference below in Table 15.

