[1]: The specific criteria for stopping the GCB-DLBCL expansion cohort for futility or efficacy. For instance, if there are 20 subjects, then the trial may be stopped for futility if No. of Responders ≤ 4 , or Part 2 opened for efficacy if No. of Responders ≥ 8 .

Section 12.2.2 Part 2: Expansion Cohort

REVISED TEXT

An initial dose escalation will be used to establish the RP2D for GSK2816126. Once the final dose is confirmed, at least 12 and up to 30 subjects in both GCB-DLBCL mutation status cohorts, up to 16 subjects in both tFL mutation status cohorts and up to 37 subjects with MM will be enrolled at that dose, using decision rules defined in Figure 1, Figure 2 and Figure 3. The sample size and stopping rules are based on the methodology of Lee & Liu [Lee, 2008].

Upon completion of cohort expansion in Part 1 and the totality of data supports opening Part 2, GCB-DLBCL and tFL patients in both mutation status, as well as patients with MM will be enrolled at RP2D for Part 2 study. There are 5 cohorts in Part 2, i.e. 2 cohorts for GCB-DLBCL patients (mutant and wild type), 2 cohorts for tFL patients (mutant and wild type), and 1 cohort for MM patients.

For each of GCB-DLBCL and tFL cohorts, at least 10 subjects and up to 32 subjects will be enrolled at the RP2D (including subjects enrolled in the previous stage), using decision rules defined in Table 17. The sample size and stopping rules are based on the methodology of Lee & Liu [Lee, 2008].

The assumptions underlying the design are detailed below for both GCB-DLBCL and tFL cohorts. The null hypothesis is:

$$H_0: p \leq 20\%$$

The alternative hypothesis is:

$$H_A: p \geq 40\%$$

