As listed in Table 17, the futility/efficacy evaluation will start with 10 subjects and until maximum of 32 subjects. This design allows to stop early for futility only. The design will have a type I error rate (α) of 0.066 and a power of 0.801. The trial may be stopped early for futility if the predictive probability of the overall response rate greater than the null hypothesis of 20% is below 10% for this design. The type I error rate, power, and predictive probability of success were derived by explicitly stating null and alternative hypothesis of response rate, the minimum and maximum sample size, futility and efficacy stopping boundaries and the selection of the optimizing criterion as the maximization of power under the alternative hypothesis. The Bayesian prior used in determining the design was Beta (0.15, 0.85), a distribution with a mean response rate of 15%. Under the null hypothesis, that is, if the true response rate is 20%, the expected sample size of the design is 16.06 subjects and probability of early termination (PET) is 90.8%. Under the alternative hypothesis, that is, if the true response rate is at least 40%, the expected sample size of the design is 29.16 subjects and PET is 18.1%.

The input parameters for the design shown in Table 17 are:

Nmin	10
Cohort	1
Nmax	32
theta_Lbegin	0.1
theta_Lend	0.1
theta_Lstep	0.001
theta_Upper	1
theta_Tbegin	0.9
theta_Tend	0.9
theta_Tstep	0.001
p_0	0.2
p_1	0.4
Prior a0	0.15
Prior b0	0.85
Type I Error	0.1
Power	0.8

Table 17 Stopping Rules for GSK2816126 GCB-DLBCL and tFL Cohort Expansion in Part 2

Number of evaluable subjects	Stop for Futility if No. of Responders (CR+PR) Less Than or Equal To This Number
10	1
11	1
12	2
13	2
14	2
15	3
16	3
17	3
18	3
19	4
20	4
21	4
22	5
23	5
24	5
25	6
26	6
27	6
28	7
29	7
30	8
31	8
32	9

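### The type I error of 0.066 and power of 0.801 stated for Part 2 describe a stand-alone cohort, but the two GCB-DLBCL cohorts carry in the Part 1 subjects whose responses decide whether Part 2 opens

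*Protocol*

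**What the plan says.** All references are to the revised text of Amendment 5, the last amendment shown.

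- **Carry-over.** Section 3.4 states that GCB-DLBCL, tFL and MM patients treated at the MTD/RP2D in the preceding stages ("dose escalation and cohort expansion in Part 1) will be included for the Part 2 analysis"). Section 12.2.2 repeats this for each lymphoma cohort: at least 10 and up to 32 subjects "will be enrolled at the RP2D (including subjects enrolled in the previous stage), using decision rules defined in Table 17".
- **Opening of Part 2.** Section 12.3.4.1: "If success criteria are reached at an interim analysis for GCB-DLBCL" at the MTD/RP2D, "and the totality of data support opening Part 2, then Part 2 will begin and Part 1 expansion will close". Section 3.3.7 words this more softly (Part 2 may be opened), and the criteria are the Table 16 boundaries for 13 to 27 subjects.
- **Same null.** Section 12.1.2 gives the four Part 2 lymphoma cohorts the same hypotheses as Part 1: 20% or less against 40% or more.
- **Stated performance.** Section 12.2.2 says the Table 17 design will "have a type I error rate (α) of 0.066 and a power of 0.801".
- **Case mix.** Section 3.5.2 enrols Part 1 GCB-DLBCL subjects whatever their EZH2 status, and puts the share of GCB-DLBCL with an activating mutation at about 22%.
- **Numbers.** Section 12.2: "Approximately 168 subjects will be enrolled in Part 2 in five expansion cohorts", described there as additional to Part 1.

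**The concern.** When Part 2 opens because the Part 1 GCB-DLBCL cohort crossed its efficacy boundary (6 of 13, for example), those subjects have an observed response rate well above 20% whatever the truth is. They are then counted again in the wild-type and mutant cohorts and tested against the same 20%. The protocol describes no allowance for this. A reader of a positive Part 2 wild-type result would attach the stated 6.6% false-positive rate to it, although much of the evidence is the Part 1 result a second time. Overall response rate is the Part 2 primary endpoint, so the estimate is affected too.

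**Working it through.** **Inputs.** Table 16 (Part 1, 13 to 27 subjects, futility and efficacy boundaries). Table 17 (Part 2, 10 to 32 subjects, futility only, success at 10 or more responders of 32). True rates 20% and 40%. Mutant share 22% from Section 3.5.2; using it as the Part 1 case mix is an assumption, varied below.

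**Step 1: reproduce the plan.** Let S(n, r) be the probability of Part 2 success with r responders in n subjects, and b(n) the Table 17 boundary.
- S = 0 if n ≥ 10 and r ≤ b(n).
- S(32, r) = 1 if r ≥ 10.
- Otherwise S(n, r) = p·S(n+1, r+1) + (1−p)·S(n+1, r).

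Starting from S(0, 0), this gives 0.0660 at p = 20% and 0.8007 at p = 40%. Expected sizes are 16.06 and 29.16, and early termination 90.8% and 18.1%. All match Section 12.2.2. The same recursion on Table 16 gives 0.0865 and 0.8031 with expected sizes 16.48 and 16.98, matching the stated 0.087, 0.803, 16.48 and 16.98. The stated Part 2 pair is therefore that of a cohort starting empty.

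**Step 2: chain the parts.** Run Part 1 under Table 16, with each subject wild type with probability 0.78. Let π be the probability of each state in which the efficacy boundary is crossed. Carry that state's n and r for the genotype into Table 17 and add fresh subjects up to 32:
- given opening: Σ π·S(n, r) / Σ π
- jointly with opening: Σ π·S(n, r)

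Σ π is 0.0865 at 20% and 0.8031 at 40%.

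| True rate | Cohort | Success given opening | Joint with opening | Mean observed rate given opening |
|---|---|---|---|---|
| 20% | Wild type | 0.447 | 0.039 | 29.5% |
| 20% | Mutant | 0.139 | 0.012 | 21.2% |
| 20% | Stand-alone | 0.066 | n/a | 16.4% |
| 40% | Wild type | 0.936 | 0.752 | 41.8% |
| 40% | Mutant | 0.829 | 0.666 | 38.8% |
| 40% | Stand-alone | 0.801 | n/a | 37.8% |

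Check: 0.0865 × 0.447 = 0.039 and 0.8031 × 0.936 = 0.752. At a true rate of 20%, a Part 1 cohort that crosses its boundary shows a mean response rate of 42%. About 14.4 wild-type subjects with 5.8 responses are then carried in.

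**Step 3: sensitivity at a true rate of 20%, given opening.**
- Mutant share 40% to 10%: wild type 0.32 to 0.55, mutant 0.22 to 0.10.
- Part 1 looks at 13/20/27, at 20/27 or at 27 only, or non-binding futility: wild type 0.45 to 0.52.
- Wild type 20% but mutant 40%: wild type 0.27. With mutant 60%: 0.18.

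**Step 4: new subjects only.** Given opening, 0.066 and 0.801 hold again. The joint probability of success at 40% is 0.8031 × 0.8007 = 0.643.

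**Step 5: totals.** 4 × 32 + 40 = 168, and 40 + 27 + 15 + 168 = 250, the stated maximum. That sum counts 32 new subjects per lymphoma cohort, whereas Section 12.2.2 places earlier subjects inside the 32.

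**The case against.** The strongest reply is that type I error ordinarily means the chance of declaring success for an inactive drug. Over the whole sequence that chance is 0.039 and 0.012, below 0.066. This stands. A reader might infer from the 0.45 that the trial's false-positive control is broken, and the documents do not support that: the 0.45 applies only on a branch that an inactive drug reaches with probability 0.087. If the mutant rate is 40% while wild type is at 20%, the joint wild-type figure is 0.057. It cannot exceed 0.090, the chance of 10 or more responders in 32 with no interim look.

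Other stronger readings also fail.
- **Only responders are re-used.** All subjects at the MTD/RP2D are carried over. The distortion comes from conditioning on Part 1 success.
- **The pooled rate is always inflated.** At a true 40% the wild-type mean is 41.8%, an error of +1.8 points. A stand-alone cohort gives 37.8%, an error of −2.2 points.
- **All Part 2 cohorts are affected.** The tFL and MM responses do not decide opening, so Table 18 and the tFL use of Table 17 are not distorted by this mechanism.
- **The pooling must go.** The shortfall in joint power comes from the Part 1 success criterion. Carry-over partly offsets it (0.752 and 0.666 against 0.643).
- **The totals contradict the pooling.** They are worded as approximate ceilings and may overlap, so this is a point to clarify.

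It is also fair that opening involves a totality-of-data judgement, that interim procedures are deferred to the Reporting and Analysis Plan, and that the 0.45 assumes equal rates in both genotypes. None of this rescues the stated pair, because the protocol itself fixes both the carry-over and the error rates.

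**Conclusion.** The point holds for the two GCB-DLBCL cohorts. The figures 0.066 and 0.801 are correct arithmetic for a design these cohorts do not follow, and in the base case they describe neither cohort, whether read given opening or jointly with it. Given opening, an inactive drug would succeed in wild type about 45% of the time, with an observed rate averaging about 29% against a true 20%. Jointly, false-positive rates are lower than stated, and so is power at 40% (0.75 and 0.67). The base case assumes a 22% mutant share, equal response rates in both genotypes and boundaries followed as tabulated. Every alternative tried leaves the conditional wild-type figure well above 0.066. The harm lies in how a Part 2 GCB-DLBCL result would be interpreted, and the overall sequence is not anti-conservative.

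**What to change.** For the GCB-DLBCL cohorts only:

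1. In Section 12.2.2, state that 0.066 and 0.801 apply to a stand-alone cohort. For GCB-DLBCL, replace them with the conditional and joint figures of the Part 1-to-Part 2 sequence, with the assumed mutant share and its range.
2. In Sections 3.4 and 12.2.2, require the response rate among newly enrolled Part 2 subjects to be reported beside the pooled rate, and label the pooled rate as selected on Part 1 success.
3. In Sections 5.1 and 12.2, state whether the 168 Part 2 subjects include or exclude those carried over.

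These are wording changes and one extra summary, with no added subjects. Testing only newly enrolled subjects is an option: it restores 0.066 and 0.801 given opening and fits the stated total of 250. It gives up any saving from counting the 13 to 27 Part 1 subjects, and it lowers the joint probability of success at a true 40% to about 0.64. That is a trade-off for the sponsor and is not needed to correct the text.

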Interim analysis (IA) of futility and efficacy can be conducted at any time after 13 GCB-DLBCL subjects have enrolled and are evaluable for response assessment. If the thresholds for futility are met, the Part 1 expansion cohort may be stopped based upon the evaluation of the totality of the data. If the efficacy thresholds are reached, then Part 2 expansion may be opened. If neither futility nor efficacy thresholds are met at any interim analysis, and the totality of the data does not support continuation of the trial, then the trial may be terminated. All available data will be considered in making decision of termination or continuation of the trial.

Section 3.4 Part 2: Expansion Cohorts

Rationale for Change: Due to the improvement of response rates of cancer treatments over time, the study designs in Part 2 expansion phase based on predictive probability method were revised by updating the null and alternative hypothesis, to align with the current typical response rates. The sample size and futility stopping criteria for each cohort (GCB-DLBCL mutant and wild type, tFL mutant and wild type, and MM) are updated. Additional details were moved to Section 12, Data Analysis and Statistical Considerations, of the protocol.

REVISED TEXT

Part 2: Expansion Cohorts in both wild type and EZH2 mutation-positive GCB-DLBCL and tFL subjects, and subjects with MM

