Table 15 Statistical Basis for Phase I Dose Escalation in a 3+3 Scheme

True incidence of dose-limiting toxicity	10%	20%	30%	40%	50%	60%
Probability of escalating the dose	0.91	0.71	0.49	0.31	0.17	0.08

Section 12.2.1.2 Cohort Expansion in Part 1

For GCB-DLBCL expansion cohort in Part 1, futility and efficacy evaluation of response data will be performed in order to support the early decision of Part 2 expansion. The sample size and stopping rules are based on the predictive probability methodology of Lee & Liu [Lee, 2008]. The predictive probability design is similar to a two-stage design in that it allows for early termination of the trial due to either futility or efficacy. The differences are that the predictive probability design allows for evaluation of stopping rules on an on-going basis, once a minimum number of subjects are evaluable, rather than at only two stages. While the two designs have comparable type I error rates and power, the probability of early termination is greater with the predictive probability design compared with two-stage design.

The detailed decision rules of the design for Part 1 expansion cohort are listed in Table 16. The decision rules to stop the trial for either futility or efficacy were constructed as follows:

- If Predictive probability of response greater than the null hypothesis θ_L , then stop the trial and reject the alternative hypothesis (i.e., claim futility); and
- If Predictive probability of response greater than the null hypothesis θ_U , then stop the trial and reject the null hypothesis (i.e., declare efficacy);
- Otherwise continue enrollment,

Where θ_L and θ_U are prespecified lower and upper limit of probabilities for establishing stopping criteria in terms of futility and efficacy, respectively.

The hypothesis of overall response rate (p) of GCB-DLBCL subjects for the cohort expansion design are detailed below.

The null hypothesis is:

$H_0: p \leq 20\%$

The alternative hypothesis is:

$H_A: p \geq 40\%$

As listed in Table 16, the futility/efficacy evaluation will start with 13 subjects and allow for maximum of 27 subjects (including GCB-DLBCL subjects enrolled at the RP2D in the dose escalation phase.) This design will have a type I error rate (α) of 0.087 and a

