As listed in Table 18, the futility/efficacy evaluation will start with 14 subjects until maximum of 40 subjects (including MM subjects enrolled at the RP2D in the dose escalation phase, if any). This design allows to stop early for futility only. The design will have a type I error rate (α) of 0.072 and a power of 0.814. The trial may be stopped early for futility if the predictive probability of the overall response rate greater than the null hypothesis of 10% is below 10% for this design. The type I error rate, power, and predictive probability of success were derived by explicitly stating null and alternative hypothesis of response rate, the minimum and maximum sample size, futility and efficacy stopping boundaries and the selection of the optimizing criterion as the maximization of power under the alternative hypothesis. The Bayesian prior used in determining the design was Beta (0.10, 0.90), a distribution with a mean response rate of 10%. Under the null hypothesis, that is, if the true response rate is 10%, the expected sample size of the design is 20.82 subjects and probability of early termination (PET) is 89.0%. Under the alternative hypothesis, that is, if the true response rate is at least 25%, the expected sample size of the design is 36.56 subjects and PET is 16.7%.

Starting with 13 subjects and allowing for a maximum sample size of 37, this design will have a type I error rate (α) of 0.032 and about 85% power when the true response rate is 20%. The trial is not designed to stop early for efficacy, but is designed to stop early for futility if the predictive probability of success is about 1.0% or less. The type I error rate, power, and predictive probability of success to stop early for futility were derived from explicitly stating the minimum and maximum sample size, futility stopping rate and selection of the optimizing criterion as the minimization of the power under the alternative hypothesis. The Bayesian prior used in determining the design was Beta (0.20, 0.80), a distribution with a mean response rate of 20%. Under the null hypothesis, if the true response rate is 5%, the expected sample size of the design is 22 subjects and probability of early termination (PET) is 91%. Under the alternative hypothesis, if the

~~true response rate is 20%, the expected sample size of the design is 36 subjects per expansion cohort and PET is 10%.~~

Section 12.3.3.1 Primary Comparisons of Interest

REVISED TEXT

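### The printed type I error rates assume every futility crossing stops the cohort with a review after each subject, but the text makes stopping optional and leaves look timing open

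*Protocol*

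**What the plan says.** The text is the revised wording of Amendment 5.

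**Error rates.** Each design has one type I error rate, stated without condition:
- Section 12.2.1.2 (Part 1 GCB-DLBCL expansion, Table 16): "This design will have a type I error rate (α) of 0.087 and a" power of 0.803.
- Section 12.2.2 (GCB-DLBCL and tFL, Table 17): "have a type I error rate (α) of 0.066 and a power of 0.801".
- Section 12.2.2 (MM, Table 18): "have a type I error rate (α) of 0.072 and a power of 0.814".

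**Mandatory wording.** The rule construction in Section 12.2.1.2 says that a futility crossing stops the trial and rejects the alternative. The futility columns of Tables 16 to 18 are also headed as instructions to stop.

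**Optional wording.**
- Section 3.3.7 says that when the futility threshold is met "the Part 1 expansion cohort may be stopped based upon the evaluation of the totality of the data".
- Section 3.4, on Part 2, says: "All available data will be considered in making decision of termination or continuation of the trial".
- Sections 12.2.1.2 and 12.2.2 and the Table 16 footnote use 'may' for the futility stop.

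**Timing of looks.** Section 3.3.7 and Section 3.4 allow interim analysis at any time once the minimum number is reached. The design inputs use a cohort size of 1, which means a look after every subject.

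**The concern.** A futility boundary that always stops the cohort removes some paths that would otherwise end in a false positive. If the quoted type I error takes credit for that removal, it holds only when the boundary is obeyed. Here a cohort could touch the futility count, be continued on other evidence, and later reach 9/27, 10/32 or 7/40. No passage shown says it could not then be called positive.

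Overall response rate is the primary endpoint of the five Part 2 cohorts. The protocol says the designs will have these error rates. Someone relying on 0.072 for MM would not learn that the value guaranteed by the rule as written is 0.0995, almost at the ceiling.

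**Working it through.** **Inputs**
- Table 16: n from 13 to 27, null 20%, alternative 40%, futility and efficacy boundaries. Futility is 8 or fewer at n = 27, so success is at least 9/27.
- Table 17: evaluation is to "start with 10 subjects and until maximum of 32 subjects", null 20%, alternative 40%, futility only. The last entry is 9 at n = 32, so success is at least 10/32.
- Table 18: n from 14 to 40, null 10%, alternative 25%, futility only. The last entry is 6 at n = 40, so success is at least 7/40.
- Ceiling on type I error: 0.10, in Section 12.2 for Part 1 and in the input list of each design.

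As a check, the boundaries were rebuilt from the stated Beta priors and theta values by beta-binomial predictive probability. Every entry in the three tables matched.

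**Method.** Let f(n,k) be the probability that a cohort is still running after n subjects with k responders:

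f(n,k) = (1 − p) f(n−1,k) + p f(n−1,k−1).

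At each look, remove every k at or below the futility count. For Table 16, also remove every k at or above the efficacy count and add it to the success probability. Success at the end is the sum of f(Nmax,k) over k at or above the success count.

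**Step 1: the plan's own figures.** Every crossing stops, with a look after each subject from the minimum n:

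| Design | Type I error | Power | Expected n, null / alternative | Early termination, null / alternative |
|---|---|---|---|---|
| Table 16 | 0.0865 | 0.8031 | 16.48 / 16.98 | 96.3% / 94.7% |
| Table 17 | 0.0660 | 0.8007 | 16.06 / 29.16 | 90.8% / 18.1% |
| Table 18 | 0.0721 | 0.8142 | 20.82 / 36.56 | 89.0% / 16.7% |

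All agree with the protocol at its printed precision, which identifies the assumption behind the figures.

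**Step 2: upper bound when futility is never enforced**
- Table 17: P(X ≥ 10 | n = 32, p = 0.2) = 0.0898; power 0.884. Ratio to stated: 0.0898 / 0.066 = 1.36.
- Table 18: P(X ≥ 7 | n = 40, p = 0.1) = 0.0995; power 0.904. Ratio: 0.0995 / 0.072 = 1.38.
- Table 16, efficacy stops kept and futility removed: 0.0944; power 0.834. Ratio: 0.0944 / 0.087 = 1.09.

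**Step 3: every crossing enforced, but fewer looks (Table 17)**
- Looks at n = 10, 16, 22 and 28: type I error 0.073.
- Looks at n = 10 and 20: type I error 0.080.

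For Table 17, look timing alone therefore moves the figure.

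**Step 4: partial overriding (Table 17).** This is an illustration that assumes a fixed share of crossing cohorts is continued to the end, regardless of their data. The gap is 0.0898 − 0.0660 = 0.0238.
- 10% overridden: 0.0660 + 0.10 × 0.0238 = 0.068.
- 25% overridden: 0.0660 + 0.25 × 0.0238 = 0.072.

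**The case against.** The strongest reply is that the protocol's arithmetic is correct. The printed values are the operating characteristics of the tabulated rule, Section 12.2.1.2 states that rule as mandatory, and the Part 2 design is described as similar. On that reading a crossing rejects the alternative and no later positive claim exists. This stands as far as it goes: there is no calculation error. It does not remove the conflict, because the same sections and Sections 3.3.7 and 3.4 make stopping discretionary, and nothing says which wording governs.

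Other points that stand:
- Discretion also works downwards. A Part 1 cohort may be stopped with no boundary crossed, and an efficacy crossing opens Part 2 only if the totality of data supports it. Fewer looks can also lower the Part 1 figure: a single test at 9/27 has type I error 0.074.
- The explicit totality-of-data condition on futility belongs to Part 1, where the effect is small. Part 2 rests on 'may' and the general sentence in Section 3.4.
- Section 12.3.4 calls for continuous review in Part 1 and ongoing review in Part 2, which is close to a look after each subject. It leaves interim details to the Reporting and Analysis Plan, which could settle whether futility is binding. The error rates, however, are asserted here without that condition.

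A reader might infer that the true error rates are higher than printed, or that 0.094, 0.090 and 0.0995 are the design's real rates. The documents do not support either. Those values need every crossing to be overridden, although about 91% (Table 17) and 89% (Table 18) of null cohorts cross early.

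**Conclusion.** The point holds as a mismatch between the stated error rates and the stated rule. The figures 0.087, 0.066 and 0.072 apply when every futility crossing stops the cohort and responses are reviewed after each subject. Under the optional wording, type I error can be as high as 0.094, 0.090 and 0.0995. For the two Part 2 designs, overriding or sparse looks give values between the printed figure and the bound.

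The bounds assume the tabulated success counts, independent responses with a common rate, and, for Table 16, that efficacy stops are kept. All three stay within the 0.10 ceiling, though MM has almost no margin. Power rises on the same reading. A reader might infer a breach of the design limit; there is none, and no boundary or sample size needs to move. The consequence is confined to what the protocol may claim about its false-positive rates, mainly in Part 2.

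**What to change.** In Sections 12.2.1.2 and 12.2.2, reconcile 'may' with 'stop' and align Sections 3.3.7 and 3.4. Either route is sound:

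1. **Keep futility non-binding.** State the type I error as at most 0.094 (Table 16), 0.090 (Table 17) and 0.0995 (Table 18), with power of 0.834, 0.884 and 0.904 if no futility crossing is enforced. Keep the printed type I error, power, expected sample size and early-termination figures, labelled as applying when every crossing stops the cohort with a look after each subject.
2. **Make futility binding.** State that a cohort which crosses the futility count cannot later be declared positive, and fix the looks at every subject from the minimum n. The printed figures then apply as they stand. A sparser fixed schedule would need its own recalculated figures.

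Either route costs a few sentences. The first makes the headline error rate slightly less favourable; the second gives up the freedom to claim success after continuing past a crossing.
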